Observational studies suggest that bariatric surgery is the most effective intervention for weight loss producing an average weight loss of 30-35% that is maintained in $\sim 60\%$ of patients at 5 years ⁷. This has led to a dramatic increase in the number of procedures performed annually from 13,365 in 1998 to an estimated 102,794 in 2003 ⁸. A newer procedure, sleeve gastrectomy (SG) is a restrictive operation that has been performed much more frequently of late, comprising 34% of the $\sim 110,000$ bariatric surgeries performed in 2013. SG is projected to and may become the most frequent bariatric procedure in North America ⁹. SG may be cheaper than RYGB in terms of operative costs and because it is not a malabsorptive procedure, the costs of follow-up, and care of morbidities arising from micronutrient malabsorption, should be lower ¹⁰. Bariatric surgery effectively produces sustained weight loss in obesity and is widely performed in the United States

2) Comparative effectiveness of RYGB and SG. It has been suggested that remission rate is associated with the length of bypass ($\sim 85\%$ for standard RYGB, $\sim 93\%$ for long-limb RYGB and $\sim 98\%$ with duodenal switch ^{11,12}). Recent prospective, randomized

controlled trials have however reported lower remission rates for diabetes with RYGB although, it remains superior to medical therapy¹³⁻¹⁵. Kashyap et al. has suggested that differences in fat loss and β -cell function between RYGB and SG occur ≥ 1 year after surgery¹⁶. Of the 2 studies with 3 year follow-up, one in nondiabetic subjects¹⁷ did not demonstrate clear differences in weight loss while in the other RYGB was significantly superior to SG in terms of weight and glycemic control¹⁸. The obvious anatomic differences between the procedures result in differences in enteroendocrine secretion: postprandial GLP-1 concentrations are lower after SG compared to RYGB in the comparative studies undertaken in humans^{16,19-22}. On the other hand, a liquid meal, especially after gastric restriction, may not recreate conditions present after a solid meal²³. Whether these differences can explain a divergence in metabolic outcomes remains unknown.

[figure not shown]

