We propose enrolling 60 non-diabetic adults scheduled for SG and 30 patients undergoing RYGB. Patients scheduled for SG will be randomized to receive Liraglutide (3mg daily) in a double-blind, randomized, placebo-controlled fashion (randomized in a 1:1 ratio). All participants will be followed longitudinally with serial measurement of outcome variables (weight, blood pressure, lipid profile, activity and satiety) over a three year period. Our power calculations suggest that 25 patients per group will be sufficient to accomplish our goals even with a loss of 5 subjects per group to follow up.

Bariatric Sx	2008		2009		2010		2011		2012		2013	
	ND	DM										
RYGB	107	46	166	70	160	63	207	83	184	64	210	59
AGB	9	0	27	0	10	0	34	4	8	2	3	1
SG	0	0	25	0	32	10	62	29	78	25	102	36

Table 1: Total numbers of laparoscopic surgeries performed as 1st procedure at Mayo Clinic. AGB = Adjustable Gastric Banding; ND = Non-diabetic; DM = Diabetic patients.

a) Subjects: A total of 75 patients will be recruited from the Nutrition Clinic at Mayo Clinic Rochester prior to undergoing bariatric surgery. Of these 25 will be scheduled for RYGB while the remainder (50) are scheduled for SG. Healthy status will indicate that the participant has no known active systemic illnesses or active macrovascular disease. To be eligible subjects must be willing to participate in all the studies outlined. **Baseline Visit:** Subjects will provide written informed consent. To ensure they are healthy, subjects will undergo a history and physical examination including supine and standing blood pressure; blood collection for complete blood count, HbA_{1c}, fasting lipid profile, electrolytes, hepatic panel and urine collection to exclude pregnancy in females of child bearing potential. Habitual activity levels⁴¹, and bowel symptoms⁴² will be assessed.

BMI $\geq 35 \text{ kg/M}^2$ in the presence of at least one weight-related comorbid condition including hypertension, obstructive sleep apnea or dyslipidemia. Alternatively, a BMI $\geq 40 \text{ kg/M}^2$ without comorbid conditions is deemed to confer eligibility for bariatric surgery at the Mayo Clinic.

ii. Age will be between 20 and 65 years of age.

- iii. Subjects will have no active physical illness which will interfere with mobility or weight loss after bariatric surgery.

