- iv. Prior to acceptance for surgery, patients seen in the bariatric clinic must undergo psychological assessment and complete a supervised comprehensive lifestyle program. Please refer to ⁴⁶ for details.
- v. Female subjects (randomized to study drug) who are sexually active and able to become pregnant, must agree to use birth control methods for the duration of the study

c) Exclusion Criteria:

- i. Prior use of glucose lowering medication in the 3 months prior to screening.
- ii. A fasting glucose $\geq 126\text{mg/dl}$ or an HbA1c $\geq 6.5\%$ will be taken as evidence of type 2 diabetes and therefore patients will be deemed ineligible for participation.
- iii. Prior abdominal surgery other than those that would not affect glucose metabolism, i.e., cholecystectomy, appendectomy, C-section or hysterectomy.
- iv. Pregnancy or active consideration of pregnancy during the period of study. Subjects will be discontinued if they become pregnant during the study.
- v. Hypersensitivity to liraglutide or any product components.
- vi. Personal or family history of medullary thyroid carcinoma or Multiple Endocrine Neoplasia type 2 in those who will undergo sleeve gastrectomy
- vii. Prior history of pancreatitis, cholelithiasis or cholecystitis.
- viii. Concurrent use of insulin or any other GLP-1 receptor agonist.
- ix. Active, severe psychiatric disease
- x. Pregnancy or breastfeeding

d) Surgery: Subjects will then undergo the surgery to which they had been assigned on clinical grounds. At present there are no clear guidelines in this regard and a patient is assigned to a bariatric surgical procedure based mainly on clinical factors. Clinical factors considered include the presence of specific obesity-related comorbid diseases and body mass index. Also considered are the patient's psychological complexity, social situation, and a patient's particular preference. A prior history of severe gastro-esophageal reflux is a relative contraindication to SG. **Note that the study team will play no role in that decision other than to ensure that participants in either group are matched for age, sex and BMI.** At Mayo Clinic, Rochester the standard protocol is to see patients back for care at 3, 6 and 12 months and then annually after bariatric surgery.

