e) Randomization: Subjects undergoing SG will be randomized (1:1) at the time of the 3 month visit after bariatric surgery. A double-blind design will be utilized. Liraglutide will be started at 0.6 mg SUBQ daily for 1 week. Subsequently, Liraglutide will be increased by 0.6 mg SUBQ daily on a weekly basis till the maintenance dose of 3.0 mg/day is reached. The placebo dose will also be titrated in a similar fashion. The study medication will be dispensed by the research pharmacy which will handle randomization and ensure that blinding is maintained. SG subjects will return to the CRTU for dispensing of study drug at standard follow-up visits (months 6, 12, 24, 36) and also at months 18 and 30. Subjects undergoing RYGB will return to the CRTU at standard follow up visits, months 3, 6, 12, 24, 36. Recruitment will continue till 50 subjects after SG are randomized and 25 subjects after RYGB are enrolled.

f) Study Visits: These will be timed to coincide with the standard follow-up visits at 3, 6, 12, 24 and 36 months after bariatric surgery. In addition to a history and physical examination, blood will be collected for creatinine, fasting glucose, HbA_{1c}, fasting lipid profile and hepatic panel, and urine collection to exclude pregnancy in females of child bearing potential. Supine and standing blood pressure will also be measured as well as body composition using DXA (at months 12, 24 and 36). Habitual activity levels⁴¹, bowel symptoms⁴², Stunkard's Eating Inventory⁴³, The Weight Efficacy Life-Style Questionnaire⁴⁴ & Eating and Weight Patterns-Revised⁴⁵ will be assessed. Collected data will include height, weight, blood pressure, pulse rate, medications used, and adverse events. During clinic visits, as per standard practice, subjects will meet with a dietitian and with a behavioral psychologist. Compliance will be assessed using an electronic record of food intake. The psychologist will use motivational enhancement and behavior change techniques to promote compliance with the dietary guidelines⁴⁷. In addition, to ensure compliance with instructions to increase physical activity, which will be reiterated at each visit, we will gather information about daily step counts from step-counters or smartphones.

g) Telephone follow up: The study coordinator will schedule monthly calls with each subject (or more frequently if necessary) to rapidly identify problems and help ensure compliance.

h) Early Termination

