For any patient enrolled in the study, the study participation will be concluded after the last visit at month 36, or at early termination. Should any patients withdraw or be withdrawn from the study, all of the Early Termination assessments should be completed before early termination, if possible, including; blood collection for creatinine, fasting glucose, HbA_{1c}, fasting lipid profile, hepatic panel, and urine collection to exclude pregnancy in females of childbearing potential. Supine and standing blood pressure will also be measured as well as body composition using DXA. Habitual activity levels, bowel symptoms, Stunkard's Eating Inventory, The Weight Efficacy Life-Style Questionnaire & Eating and Weight Patterns-Revised will be assessed. Collected data will include height, weight, blood pressure, pulse rate, medications used if applicable, and adverse events.

i) Power Calculation: See detailed power calculations below.

j) Adverse Event Monitoring: The most common adverse reactions associated with liraglutide use are nausea, dizziness, abdominal pain, increased lipase, hypoglycemia, diarrhea, constipation, vomiting, headache, decreased appetite and dyspepsia. Acute pancreatitis has been associated with liraglutide use. Relevant symptoms will be screened for at the time of routine follow-up as well as telephone follow-up.

1) Interpretation: We will accept our primary hypothesis that administration of 3.0mg liraglutide to participants after SG increases weight loss compared to placebo if after unblinding, the liraglutide group has significantly greater weight-loss from baseline

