compared to the SG + placebo group. Similarly, we will reject our 2° (i) hypothesis if the weight loss observed in participants who undergo SG and receive Liraglutide does not differ from that after RYGB. Such a conclusion would support a role of GLP-1 in the weight loss achieved (and maintained) after RYGB. The questionnaires collected over the duration of the study will be utilized to help generate hypotheses related to food intake as it is affected by liraglutide use after SG compared to placebo. As before, we will determine whether the addition of liraglutide to SG improves effects of SG on cholesterol and blood pressure ¹⁵. If this indeed the case, we will accept our 2° hypothesis (ii). If the high GLP-1 concentrations observed after RYGB modulate appetite and food intake as suggested by our preliminary data (Fig. 1), we would expect weight loss after RYGB to also lower cholesterol and blood pressure. We will reject our 2° (iii) hypothesis if the blood pressure and LDL-cholesterol lowering observed in participants who undergo SG and receive Liraglutide does not differ from that after RYGB.

STATISTICAL CONSIDERATIONS:

Using JMP® Pro 11.2.1 (SAS Institute) for the power calculation we established the following: -

In a prior experiment¹⁵ we observed an overall [mean value \pm (SD)] of % weight change after RYGB = $-26.1 \pm (8.7)$ at 1 year. Assuming similar variation, 25 subjects who complete the study in each group would provide approximately 80% power (at a 2-sided 0.05 α level), to detect a 7.0% difference in weight change between SG + treatment vs. SG + placebo. An intention to treat analysis will be undertaken.

In another, as yet unpublished experiment, 12 subjects studied before and 4 weeks after RYGB lost 11.0 ± 3.4 Kg within 4 weeks. Assuming similar variation, 25 subjects per group would provide approximately 80% power (at a 2-sided 0.05 α level), to detect a difference of a 2.7 Kg in weight between groups.

Schauer et al.¹⁴ observed an overall [mean value \pm (SD)] of weight change after RYGB = $-29.4 \pm (8.9)$ Kg. Assuming similar variation, 25 subjects per group would provide approximately 80% power (at a 2-sided 0.05 α level), to detect a 7.2kg between-group difference.

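### Secondary hypotheses (i) and (iii) treat a finding of no difference from RYGB as proof of not being inferior, and (i) then takes it as evidence for GLP-1

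*Combined protocol and SAP*

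**What the plan says.** The list of 2° Endpoints states hypotheses (i) and (iii) as SG + liraglutide being inferior to RYGB, on weight loss and on blood pressure and LDL-cholesterol respectively. Section 1) Interpretation then gives the decision rules:

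- Hypothesis (i) is rejected if "the weight loss observed in participants who undergo SG and receive Liraglutide does not differ from that after RYGB". The plan continues: "Such a conclusion would support a role of GLP-1 in the weight loss achieved (and maintained) after RYGB".
- Hypothesis (iii) is rejected if the "blood pressure and LDL-cholesterol lowering observed in participants who undergo SG and receive Liraglutide does not differ from that after RYGB". No mechanistic conclusion is attached to this one.

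The rule for (i) comes straight after the primary rule, which is met if "the liraglutide group has significantly greater weight-loss from baseline" compared with SG + placebo, and it is introduced as working in a similar way. No margin, confidence-interval criterion or named test for SG + liraglutide versus RYGB appears anywhere. The only power statement for percentage weight change that names its groups is for the two SG arms. An SG + placebo versus RYGB comparison is not planned.

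On the choice of operation, section d) Surgery says "a patient is assigned to a bariatric surgical procedure based mainly on clinical factors", and that the study team only ensures matching on age, sex and BMI. On whether SG and RYGB differ at all, the background reports two studies with 3-year follow-up: one, in nondiabetic subjects, "did not demonstrate clear differences in weight loss while in the other RYGB was significantly superior to SG".

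**The concern.** Failing to find a difference is not evidence that there is none. If the rule means a two-sided test with p at or above 0.05, then smaller groups, more dropout or noisier measurements all make it easier to reject inferiority. A real shortfall against RYGB could be reported as no difference.

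The mechanistic sentence in (i) adds a second problem. To argue from this trial that GLP-1 explains part of the weight loss after RYGB, one needs a gap between SG alone and RYGB, and evidence that liraglutide narrows it. The rule asks for neither. It can be met when the trial's own randomised comparison shows no liraglutide effect, or when SG and RYGB never differed. The second case is realistic on the plan's own background, because the study in nondiabetic subjects, the population enrolled here, showed no clear difference in weight loss.

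Finally, the RYGB contrast is not randomised. Comorbid disease, psychological and social circumstances and patient preference also steer the choice of operation, and these are not matched.

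**Working it through.** **Inputs.** The SD of percentage weight change is 8.7 points (RYGB, 1 year) and alpha is two-sided 0.05, both from Statistical Considerations. That section also gives 25 completers per group. The enrolment figures conflict: "We propose enrolling 60 non-diabetic adults scheduled for SG and 30 patients undergoing RYGB" (30 per arm) against "Recruitment will continue till 50 subjects after SG are randomized and 25 subjects after RYGB are enrolled" (25 per arm). With or without the allowed loss of 5 per group, these give 20, 25 or 30 per group.

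**Assumptions.** The no-difference rule means p ≥ 0.05 in an unadjusted two-sample t test, and the SD of 8.7 applies to both groups. The 5-point shortfall and the margins below are illustrative; the plan supplies none for this contrast.

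**The plan's own figure.** For a 7.0-point difference with n = 25, SE = 8.7 × √(2/25) = 2.46. Power is 79.6% by the noncentral t and 81.2% by the normal approximation. The stated value of about 80% reproduces.

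**SG + liraglutide versus RYGB.** SE = 8.7 × √(2/n). The 95% CI half-width is t(0.975, 2n − 2) × SE; at n = 25 this is 2.011 × 2.461 = 4.95. The chance of a non-significant result with true shortfall d comes from the noncentral t with noncentrality d/SE; at n = 25 and d = 5 this is 5/2.461 = 2.03, giving 0.488. Non-inferiority power is for a true difference of zero at one-sided 0.025, with noncentrality margin/SE.

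| | n = 20 | n = 25 | n = 30 |
|---|---|---|---|
| 95% CI half-width (points) | 5.57 | 4.95 | 4.50 |
| 5-point shortfall called no difference | 57.5% | 48.8% | 40.9% |
| 7-point shortfall called no difference | 30.2% | 20.4% | 13.5% |
| Power to exclude a 7-point margin | 69.8% | 79.6% | 86.5% |
| Power to exclude a 5-point margin | 42.5% | 51.2% | 59.1% |
| Margin met with 80% power (points) | 7.9 | 7.0 | 6.4 |

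**Sensitivity to the SD** (n = 25, 5-point shortfall): 17.7% at SD 6, 30.3% at 7, 41.9% at 8, 51.4% at 9 and 59.0% at 10.

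**Blood pressure and LDL-cholesterol.** No SD is given, so only standardised values are possible. A true deficit of 0.5 SD is non-significant 66.2%, 59.0% and 52.2% of the time at n = 20, 25 and 30.

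**The GLP-1 sentence.** Three arms were simulated 40,000 times with n = 25, SD 8.7 and no liraglutide effect:

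| True state | Rule as written supports GLP-1 | Rule met and liraglutide significantly better than placebo |
|---|---|---|
| SG 5 points short of RYGB | 48.6% | 2.2% |
| SG equal to RYGB | 95.1% | 1.9% |

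**The case against.** Five points do have force.

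- **The size of the example.** The only difference the plan powers on this scale is 7.0 points. At that size and 25 per group the error is 20%, an ordinary type II error. The 5-point example is a choice. This is fair, and is why both rows are shown. It does not rescue the rule, which names no difference worth excluding.
- **The test is inferred.** The plan does not say that no difference means p ≥ 0.05, and it might adjust for covariates. If covariates correlated 0.5 with outcome, the SD would fall to 8.7 × √(1 − 0.25) = 7.5 and the 49% to about 37%. The percentages are therefore conditional. The absence of a rule is not.
- **The GLP-1 sentence is modest.** It speaks of support rather than proof, and the liraglutide–placebo result would be reported beside it. The 95% figure is simply 1 − alpha. That lowers the practical risk of a misreading, but the plan still does not make the statement depend on the randomised result.
- **Confounding is limited by eligibility.** Diabetes, active severe psychiatric disease and active systemic illness are excluded, and all candidates have a psychological assessment. This narrows the differences between the operations' patients without removing them.
- **These are secondary comparisons.** This is true and it limits the severity. However, the RYGB group is a third of enrolment and serves only these comparisons.

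**Conclusion.** The point holds: the rules for (i) and (iii) are wrong as written, because followed literally they can lead to a false conclusion. At the plan's 25 completers per group, a 95% CI of about ±4.9 points cannot separate equality from a shortfall of several points, and a 5-point deficit would pass as no difference about half the time. For (i), the rule can credit GLP-1 when liraglutide does nothing.

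The absence of a margin or decision rule, and the missing conditions on the GLP-1 statement, are plain from the text. The percentages rest on the non-significance reading and on a 1-year RYGB SD. Follow-up runs to 36 months, for which no SD is given. The primary analysis, the sample size and the data collection are not affected. The change should be made, but it does not put the trial's main result in doubt.

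**What to change.** 1. In (i) and (iii), replace the no-difference rule with the estimated difference and its 95% CI at a named visit. Claim that SG + liraglutide is not inferior to RYGB only if the CI excludes a stated margin; otherwise report the result as inconclusive. For (iii), say which blood pressure measure is used and whether blood pressure and LDL-cholesterol must both meet their margins. Fix the margins before any outcome data are reviewed. Doing so before unblinding would be too late, because the RYGB group takes no blinded drug and its results are visible throughout. If no margin can be justified, label the RYGB comparisons descriptive.
2. Delete the GLP-1 sentence. Alternatively, keep it as hypothesis-generating, and only when SG + placebo falls short of RYGB and the randomised comparison shows that liraglutide narrows that gap. Add the SG + placebo versus RYGB contrast.
3. Adjust the RYGB contrasts for the pre-surgery value of the outcome, age, sex and BMI, and where numbers allow for recorded comorbidity and lipid or blood pressure medication. State that residual confounding remains.

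The cost is protocol and SAP wording plus one contrast on data already collected, with no extra patients. The downside is that some results that would have been called no difference become inconclusive. With 25 per group and an SD of 8.7, a margin much below 7 points is unlikely to be met.
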